1. OVERVIEW AND OBJECTIVES

The **long-term objectives** of this research are to perform large-scale randomized clinical trials (RCT) with SISU mouth guards and SOVA night guards. Towards these long-term ends, the present proposal represents investigations into the most immediate issues that can be addressed in a preliminary study. The **outcome variables** for the present study fall into four categories: (1) fabrication efficacy, (2) compliance, (3) functional efficacy, and (4) user satisfaction. The **immediate goals of this preliminary proposal** will: (1) focus on the SOVA night guard, (2) conduct *in vivo* tests of the SOVA device under controlled clinical conditions, and (3) evaluate compliance and functional efficacy in the 'natural' environment of the patient's home. The clinical application involves protection of dental structures during nocturnal parafunction (sleep bruxism). Because of the potential co-morbidity of bruxism with temporomandibular disorders (TMD), a triad of masticatory myalgia, TM joint noises and/or joint arthritides, TMD signs and symptoms will be considered in future studies. **Future goals** will involve pursuing funding to perform large-scale RCT with both the SISU and SOVA night guards.

Specific Aim 1. Compare the SOVA night guard to the custom-acrylic bite splint in clinical laboratory conditions. Hypothesis: There will be no significant differences between the devices in terms of fabrication efficacy, functional efficacy or user satisfaction.

Specific Aim 2. Compare the SOVA night guard to the custom-acrylic bite splint under ecologically relevant conditions, i.e., the home environment. Hypothesis: There will be no significant differences between the devices in terms of compliance or functional efficacy.

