2. BACKGROUND AND SIGNIFICANCE

Bite splints and bruxism. Tooth wear is an extremely prevalent condition, with > 4 teeth per dentition showing significant wear in over 50% of the population, and the prevalence increases with age to 60% by the 7th decade of life (Cunha-Cruz et al., 2010). Moreover, patients who have a history of previous bite splint wear have higher rates of tooth wear (Cunha-Cruz et al., 2010), suggesting that early intervention and long-term splint wear are required to reduce the impacts of bruxism.

Bite splints and TMD. Recent evidence suggests that bite splint use is efficacious in reducing pain symptoms in TMD patients who have been wearing splints for 1 – 6 months; however, within 15 days of terminating splint use, symptoms return (Rehm et al., 2012). These authors conclude that terminating bite splint use in TMD patients is not recommended. If this is correct, then bite splints for TMD symptom management require long-term, perhaps permanent, use. Given that no oral devices are permanent and that custom acrylic orthotics are expensive to replace, there exists a need for an alternative that is feasible in terms of cost, reliability, and regular replacement.

Current standards. There are three recognized oral devices (Maeda et al., 2009), (1) a stock type, which does not adjust to an individual's dentoskeletal morphology, (2) the mouth-formed or boil and bite type and (3) the custom-made appliance. The first two types are over-the-counter (OTC) devices. Bite splints for use with TMD and bruxism are most often custom-made. Either custom-made or the boil and bite type are most often used as mouth guards in contact sports.

Evidence varies as to which of the three oral devices is superior. Most experts presently recommend the custom-made mouth guards for sports purposes (Maeda et al., 2009). For sleep bruxism, custom-made hard acrylic or boil and bite night guards are apparently equally efficacious (Klasser et al., 2010). Finally, a review of RCTs indicates that hard acrylic orthotics were superior to soft appliances or repositioning appliances in managing TMD pain (Friction et al., 2010).

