3. METHODS AND STUDY DESIGNS

3.1 Subjects. Sample size estimations (**Table 1**) are based upon a recent review of RCTs for bruxism management, in which acrylic appliances were evaluated (see Appendix 2 in (Huynh et al., 2007)). The mean \pm 1 SD number of bruxism episodes per hour with an occlusal splint (the gold standard) was 3.97 ± 0.58 , and for a palatal splint, the mean \pm 1 SD was 4.45 ± 0.63 . Using these means and the higher SD (0.63), along with an $\alpha = 0.05$ and $\beta = 0.8$, I determined that a study would be sufficiently powered with sample sizes of 29 per group. Based on other Michigan studies, I have estimated recruitment, exclusion and attrition rates, which suggest an estimated initial screening sample size of 120 necessary to end up with 29 per group (**Fig. 1**). There will be two treatment groups: a group receiving supervised training in the fabrication of the SOVA night guard (SOVA) and a group receiving the Michigan custom-acrylic bite splint (MI BS). Two groups times 29 subjects per group equals 58 total needed for analysis (**Fig. 1**, bottom).

Table 1. Treatment (Tx) groups & sample sizes (N).

[figure not shown]
Tx	SOVA	MI BS
N	29	29

Care will be taken to match the randomized groups for age, ethnicity, gender and TMD signs/symptoms. Alternatively these will be modeled as nuisance variables if attrition rates create bias and/or there is a lack of sufficiently sized screening pools. Subject inclusion criteria will be: (1) adults, male or female, (2) clinical signs of dental wear, (3) report from significant others of nocturnal grinding and clenching noises from potential subject, (4) absence of outstanding dental and medical conditions, including cardiovascular disease, sleep apnea, and diagnosed sleep disorders, (5) full dentition sans 3rd molars, (6) no movement or neurological disorders, (7) no active orthodontics, (8) no outstanding or previous periodontal problems, (9) no removable prostheses, (10) no medication use with movement disorders as known side effects, (11) ability to follow instructions, (12) ability to report to the clinical laboratory at appointed times over the course of the study. The presence or absence of TMD joint noises or masticatory myalgia will be permitted; however, joint arthritides will not be permitted.

3.2 Project design.

Fig. 2 provides an overview of the project flow. Each aspect will be described below.

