3.2.1 Screening. Candidates will undergo a screening to assess co-morbidities and to identify inclusion and exclusion criteria. Standard questionnaires and screening instruments include the Research

Diagnostic Criteria for TMD (TMD-RDC) (Dworkin and LeResche, 1992), Jaw Function Limitation Scale (JFLS) (Ohrbach et al., 2008), the TMD Pain Screener (Gonzalez et al., 2011), Measure of Symptoms Sleep Scale (MOS), Perceived Stress Scale (PSS). Additionally, a brief clinical exam will be performed to evaluate dental and medical health, including an intra-oral and extra-oral head and neck examination, heart rate and blood pressure. Subjects meeting the acceptance criteria will be randomly assigned to one of the two groups (**Table 1**) using stratified randomization procedures (Suresh, 2011). Subjects will then have alginate impressions taken, and impressions will be poured up in stone. The models will be used either to fabricate the MI BS or to assess SOVA appliances for fabrication efficacy.

3.2.3. Splint delivery. For the SOVA group, subjects will be asked to fabricate SOVA devices in the clinical laboratory while receiving feedback from trained and calibrated study ‘instructors’. Fabrication will proceed according to manufacturer instructions. Calibrated instructors will be blinded to the study’s objectives, as will subjects. A “Michigan” acrylic bite splint will be fabricated using standard clinical practice and checked for fit and quality on subjects assigned to the MI BS group.

3.2.4 Subjective fabrication assessment. Standardized questionnaires will be provided to participants and will cover issues of ease of fabrication, ease of instructions, and other related issues for the devices. Box scales will be used to evaluate items individually and separately.

3.2.5 Quantitative fabrication assessments. Four aspects of fabrication will be evaluated by investigators: (1) stability—does the device move independently of the maxilla and is the mandible stabilized by the device, (2) retention—does the device resist displacement, (3) tissue adaptation—how much spacing exists between the maxilla and the device and between the device and mandible, and (4) health of the teeth, gingival, tongue, palate and lips.

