3.2.5a. Stability and retention will be quantitatively assessed with jaw movement (custom jaw tracking devices in conjunction with a MaxTraq motion analysis system [Innovision, Columbiaville, MI] and EMG [LabChart, ADInstruments, Colorado Springs, CO] data) and force sensors (T-scan, Tektronix, South Boston, MA). For position-stability assessment, maxilla, mandible and the splint will be simultaneously recorded from at least three sites each (to capture 6 degrees of movement freedom). Subjects will clench, grind, perform closed border movements and vacuous chewing (verified with EMG and force sensors). For retention assessment, subjects will perform a series of tests designed to dislodge the device, e.g., tapping, forced blowing, coughing, chewing on gum. Stability and retention indices will be created based on whether device movements vary independently of jaw movements and applied bite forces, and how force sensor output varies during dislodgement exercises. (Note, the force sensors will be placed between the device and the maxilla, so that reductions in sensor output will indicate that the device is being dislodged.) Deviations will be used to form standardized indices of stability and retention, with smaller values representing greater stability and retention.

3.2.5b. Tissue adaptation will be assessed by using a 3D laser scanner. The occlusal, facial and lingual surfaces of the upper arch will be scanned as will the inner surface of the night guards. An index of

[figure not shown]

Fig. 2. Overview of planned studies (see text).

adaptation will be developed based on the volumetric spaces separating the teeth from the device, using topological software. Smaller volumes will represent better tissue adaptation. Volumetric indices will be compared between devices via ANOVA or appropriate statistical methods.

3.2.5c Tissue health will be assessed via appropriate, standard methods currently used in cariology and periodontology clinical studies (Monse et al., 2012; Tirapellia et al., 2010). Baseline measurements will be compared with post-device wear measurements. Between-group differences will be studied with a repeated measures ANOVA or appropriate statistical methods.

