Table 2. Summary of objectives, methods and when performed		
Assessment	Method or modality (equipment)	When
Subjective fabrication	Questionnaires (na)	Step 2
Stability	Performance during jaw function, bite force and muscle use (MaxTraq + EMG + T-Scan)	Steps 2, 4, 5
Retention	Shape conformity (3-D laser scanner, topology)	Steps 4,5
Tissue adaptation	Tooth wear and gingival health (standard dental)	Steps 4,5,6
Tissue health		
Compliance	Self-report (questionnaires), Evidence of nocturnal use (EMG-sleep + microwear)	
Functional efficacy	Bruxism/TMD evidence, dental changes (EMG-sleep + 3-D scanning + microwear)	
User satisfaction	Questionnaires (na)	

3.2.9 Repeated measures (Step 4 Week 1 check-up and Step 5 4 Month check-up). Compliance, stability, retention, tissue adaptation and health, functional efficacy and user satisfaction will be assessed two times, viz., 1 week after delivery and 4 months after delivery (Fig. 2, Table 2). This will provide a

rigorous data set, reduce subject attrition and thus allow for both publications and further proposal applications to be pursued.

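### Tissue health (3.2.5c): a baseline is planned, but the analysis does not commit to it as a covariate, which gives up precision in the device comparison

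*Combined protocol and SAP*

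**What the plan says.** Section 3.2.5 lists tissue health as the fourth of its fabrication assessments, covering "health of the teeth, gingival, tongue, palate and lips". Section 3.2.5c says "Baseline measurements will be compared with post-device wear measurements", and for the device comparison "Between-group differences will be studied with a repeated measures ANOVA or appropriate statistical methods". Section 3.2.9 adds that tissue health, with other outcomes, "will be assessed two times, viz., 1 week after delivery and 4 months after delivery".

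The only covariates mentioned anywhere are in 3.1: age, ethnicity, gender and TMD signs/symptoms. They enter conditionally: "Alternatively these will be modeled as nuisance variables if attrition rates create bias", or if the screening pool is too small. The baseline value of the outcome is not among them. Section 3.2.1 says that randomisation is stratified.

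No section says whether the tissue-health comparison is made at 4 months or over both follow-up visits. No scale, SD, effect size or correlation is given for tissue health.

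**The concern.** If baseline enters the repeated measures ANOVA as a level of time, the device effect is the group-by-time term, in essence a comparison of change scores. If the repeated measures are only the two follow-ups, the device effect is an unadjusted comparison of post-wear values. Both are valid, but neither makes the best use of a baseline that is to be collected anyway.

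Tissue health is an outcome on which a device could show harm to teeth or soft tissue. Specific Aim 1 expects that "There will be no significant differences between the devices in terms of fabrication efficacy, functional efficacy or user satisfaction". With 29 per arm the interval for the device difference will be wide, and a wide interval is easily read as agreement. A narrower one helps the reader judge what has been ruled out, although it does not cure the reliance on a non-significant result, which is a separate matter. The open wording also leaves both model and contrast to be chosen after the data are seen.

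**Working it through.** **The plan's own figure.** Section 3.1 gives means 3.97 and 4.45 and SD 0.63 for bruxism episodes per hour. The difference is 0.48 and d = 0.48/0.63 = 0.762. A two-sided t-test at alpha 0.05 with 80% power needs 28.04 per group, so 29, as stated; power at 29 is 81.4%. This is a bruxism calculation; there is none for tissue health.

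**Assumptions.** 29 per arm (3.1); a continuous measure; equal variances; one common correlation r between any two visits, taken as 0.3, 0.5 and 0.7. None of these r values comes from the documents.

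**Per-subject variance, in units of the outcome variance.** Estimating one baseline slope with N = 58 multiplies the adjusted variance by 1 + 1/(58 − 4) = 55/54 = 1.0185.

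| Contrast | Change score | Unadjusted | Baseline-adjusted |
|---|---|---|---|
| 4 months | 2(1 − r) | 1 | (1 − r²) × 55/54 |
| Mean of both visits | 1.5(1 − r) | (1 + r)/2 | ((1 + r)/2 − r²) × 55/54 |

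**Adjusted relative to change score.**
- 4 months: (1 + r)/2 × 55/54 = 0.66/0.76/0.87.
- Mean of both visits: (1 + 2r)/3 × 55/54 = 0.54/0.68/0.81.
- Adjustment is better while r is below 108/55 − 1 = 0.96 at 4 months, and below (3 × 54/55 − 1)/2 = 0.97 for the mean.

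A simulation of 20,000 trials per r gave 0.659/0.768/0.863 and 0.543/0.685/0.812.

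**Adjusted relative to unadjusted.**
- 4 months: (1 − r²) × 55/54 = 0.93/0.76/0.52. Break-even is r² = 1/55, so r = 0.13.
- Mean of both visits: break-even solves 110r² − r − 1 = 0, so r = 0.10.
- Worst case, r = 0: variance is 1.9% larger.

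**95% CI half-width in SD (r = 0.3/0.5/0.7), t × √(2 × variance/29), with 56 df, or 55 df if adjusted.**

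| Contrast | Change score | Unadjusted | Adjusted |
|---|---|---|---|
| 4 months | 0.62/0.53/0.41 | 0.53/0.53/0.53 | 0.51/0.46/0.38 |
| Mean of both visits | 0.54/0.46/0.35 | 0.42/0.46/0.49 | 0.40/0.38/0.32 |

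**Power for an assumed 0.5 SD effect, equal at both visits.**

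| Contrast | Change score | Unadjusted | Adjusted |
|---|---|---|---|
| 4 months | 35/46/68% | 46/46/46% | 49/57/74% |
| Mean of both visits | 45/58/80% | 64/58/53% | 70/75/87% |

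Within each row, adjustment has the highest power at every r shown. Across rows it need not.

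**Choice of contrast.** Between the two adjusted analyses, the mean of both visits has more power only if the 1-week effect is at least 2√(((1 + r)/2 − r²)/(1 − r²)) − 1 = 57/63/68% of the 4-month effect.

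**Near-floor score.** For an assumed four-category score (80/12/6/2% at baseline, latent shift 0.5 SD, 10,000 trials per r), simulated 4-month power is 0.232/0.277/0.361 for change, 0.304/0.303/0.292 unadjusted and 0.305/0.326/0.387 adjusted.

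**The case against.** The strongest reply has four parts.

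- **The wording already allows this, and the planned test is valid.** True. A reader might infer that the plan rules out baseline adjustment, or that its analysis is biased. The documents support neither: the method is left open, and under randomisation the change-score and unadjusted comparisons are unbiased.
- **The 4-month change score is only one reading.** True. The heading of 3.2.9 ties the repeated measures to the two follow-ups, which points to an unadjusted mean of both; adjusting that contrast moves the half-width only from 0.42 to 0.40 SD at r = 0.3. With baseline as a third time level, the group-by-time test has 2 degrees of freedom and power of about 36/48/71% for 0.5 SD at both visits. It is therefore tempting, but unsupported, to say that the plan needs about 44/38/34 per arm to match adjustment with 29. That follows from 29 × 2(1 − r)/((1 − r²) × 55/54) and holds only against a 4-month change score at assumed correlations.
- **Fixing the contrast at 4 months can lose power.** True. With equal effects at both visits, the adjusted 4-month contrast (49/57/74%) falls below the unadjusted mean of both visits at r = 0.3 (64%) and below the change to that mean at r = 0.7 (80%). A reader might infer that adjusted 4-month analysis beats whatever was planned. It does not: the covariate and the contrast are separate choices, and the gain claimed here is only from the covariate.
- **The gain may be small in this population.** It may. Section 3.1 requires "no outstanding or previous periodontal problems", so scores may cluster near the best value with little baseline variation, and the near-floor results show only a modest gain.

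What survives is that, for any fixed contrast on a continuous measure, adjustment costs at most about 2% of variance and usually gains more.

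**Conclusion.** The point holds as a matter of efficiency. Section 3.2.5c collects the covariate but does not commit to using it as one. For a continuous measure, adjusting a fixed contrast cuts variance by about 34/24/13% against the change score at 4 months, and by about 46/32/19% for the mean of both visits, at assumed r = 0.3/0.5/0.7. Against unadjusted follow-up values the gain grows with r and disappears below about 0.13 at 4 months.

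These sizes rest on equal variances, equal correlations and 29 per arm with complete data. The trial's own correlation and scale are unknown, so the direction is firm and the size is not. In a preliminary study sized on bruxism episodes, this is a desirable change and not an essential one.

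**What to change.** In 3.2.5c, replace the analysis sentence with wording such as:

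> Tissue health is measured before device delivery. Each continuous tissue-health score at 1 week and 4 months is analysed in a linear mixed model with device, visit, device-by-visit, baseline score, baseline-by-visit and the stratification factors. One device contrast (4 months, or the mean of both visits) is named before data are seen and reported with its 95% CI.

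The pre-delivery statement is needed because 3.2.9 lists only post-delivery visits, and Table 2 and Fig. 2 cannot be read reliably in the copy available. The stratification factors should be listed by name.

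The contrast should follow the question. Four months suits an interest in longer wear, in keeping with the background's view that "early intervention and long-term splint wear are required to reduce the impacts of bruxism". The mean of both visits suits an effect expected to be similar at each.

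If a chosen measure proves ordinal or a count, include its baseline value in a model suited to that scale. A proportional-odds estimate is then conditional on baseline, so it is not the same quantity as an unadjusted one. Those models are best specified once the measures are named.

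Cost: analysis wording only, with no new visits or measurements. Each baseline slope takes one degree of freedom, about 2% of variance; the stratification terms take further degrees of freedom, not included in that 2%.

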Funds are being requested to purchase software to analyze tooth and bite splint wear, which are critical for evaluating tissue health, compliance and functional efficacy. The prices reflect large academic price reductions. Laboratory fees are needed for fabrication of the Michigan bite splints necessary for the "gold standard" control group of subjects. The microscope provides an essential and inexpensive means of quality-screening the microwear on stone models before they are shipped for analysis with the confocal microscope (see Other Expenses, below). The use of an inexpensive microscope in the [name] laboratory will effectively reduce the costs of the latter analysis by over \$2000, thus reducing budget costs by at least \$1700.

Other software as well as dental and technical supplies (> \$19,000 worth), which are necessary for successful completion of the project, will be purchased through other funding sources.

Other Expenses

Subject fee expenses have been calculated as \$20 per visit. As Fig. 1 shows, we estimate that 70 subjects will finish the first appointment. After accounting for dropouts, we estimate that 64 will finish the next two appointments. Hence the fees are calculated as shown on the budget page.

Confocal microwear processing fees are requested. These fees reflect a negotiated \$45 / subject rate, and since these microwear processing can be done after other analyses, we can target only those 58 subjects that will be included in the final analysis (Fig. 1, bottom). The processing is necessary to evaluate and fulfill the compliance and functional efficacy aspects of the project.

Indirect costs have been figured based on the modified total direct cost rate (i.e., less equipment) and at 8% as per Delta Dental Foundation's ICR.

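### A complete-case repeated measures ANOVA of tissue health would discard the observed week 1 values of subjects who miss month 4, which can bias the device contrast in either direction; the plan has no missing-data rule

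*Combined protocol and SAP*

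**What the plan says.** Section 3.2.5c gives the tissue-health analysis in two sentences. The first sets the comparison: "Baseline measurements will be compared with post-device wear measurements". The second sets the method: "Between-group differences will be studied with a repeated measures ANOVA or appropriate statistical methods". The ANOVA is the only specific method named, and the rest of that sentence leaves the choice open.

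Section 3.2.9 says that tissue health and the other repeated outcomes will be "assessed two times, viz., 1 week after delivery and 4 months after delivery". With baseline, that makes three occasions.

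The budget (section 5, Other Expenses) expects loss: "we estimate that 70 subjects will finish the first appointment", then "After accounting for dropouts, we estimate that 64 will finish the next two appointments". On microwear fees it adds that "we can target only those 58 subjects that will be included in the final analysis".

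The only stated response to attrition is in section 3.1 and concerns the matching variables (age, ethnicity, gender, TMD signs and symptoms): "Alternatively these will be modeled as nuisance variables if attrition rates create bias". The document has no rule for missing outcomes and no definition of the analysis set.

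**The concern.** A classical repeated measures ANOVA needs a complete row for each subject. Someone measured at baseline and week 1 who does not return at month 4 is dropped entirely, including the week 1 measurement already taken. Entering every randomised subject does not prevent this, because the method itself removes incomplete rows. Adjusting for age, ethnicity, gender or TMD status does not restore a deleted row.

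The outcome covers the teeth, gingiva, tongue, palate and lips, so it is one place where an ill effect of a device would show. Discomfort is a plausible reason to stop attending. If leaving is related to week 1 findings and differs between arms, the completers no longer give a fair comparison, even at week 1, where the leavers' data were in hand. The study hypothesis is that the devices do not differ, so a contrast distorted by who stayed could mislead in either direction.

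**Working it through.** **Expected loss.** From the budget: 70 − 64 = 6, and 6/70 = 8.6%. From 70 to the 58 in the final analysis: 12/70 = 17.1%. The text does not explain the step from 64 to 58, and Fig. 1 is not shown. The 58 equals 2 × 29, the sample size in section 3.1. That size reproduces: 2(1.96 + 0.84)² × (0.63/0.48)² = 27.0, so 28 by the normal formula, and 28.04, so 29, by the t-test (two-sided, reading the stated β of 0.8 as power). It rests on bruxism episodes and says nothing about precision for tissue health.

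If the next two appointments are week 1 and month 4 (an assumption), at most 6 subjects are lost over those visits. Only those who leave after week 1 have a week 1 value to discard.

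**Check by hand, binary outcome.** The documents give no tissue-injury rates. Assume 35 per arm and week 1 injury of 30% with SOVA and 10% with MI BS. The expected injured are 10.5 and 3.5, and the true contrast is 0.20. The complete-case rate in an arm is (injured − injured lost)/(35 − all lost).

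| Who misses month 4 | SOVA | MI BS | Contrast |
|---|---|---|---|
| 6 of 70, unrelated to injury | 0.300 | 0.100 | 0.200 |
| 6 of the 14 injured, same rate in both arms | 6/30.5 = 0.197 | 2/33.5 = 0.060 | 0.137 |
| 6 injured, all SOVA | 4.5/29 = 0.155 | 0.100 | 0.055 |
| 6 uninjured, all SOVA | 10.5/29 = 0.362 | 0.100 | 0.262 |
| 3 injured, all MI BS | 0.300 | 0.5/32 = 0.016 | 0.284 |

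The same true contrast of 0.20 appears as anything from 0.055 to 0.284, depending on who is lost.

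**Continuous score, two post-delivery visits.** Assumed: 35 per arm, bivariate normal scores, true difference 0.5 SD at both visits, visit correlation 0.6, month 4 missing for the subjects lost. Those lost have either the worst week 1 values or the worst values of week 1 plus equal random noise; the ranges cover both rules. Each setting used 4,000 simulated trials, and separate runs differ by about 0.01. The contrast is the complete-case device difference averaged over the two visits.

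| Loss after week 1 | Complete-case contrast (SD) |
|---|---|
| Random | 0.50 |
| 3 from each arm, worst values | 0.50 to 0.51 |
| Worst 6 of 70, one rule for both arms | 0.41 to 0.44 |
| 3 from SOVA only | 0.37 to 0.41 |
| 6 from SOVA only | 0.26 to 0.33 |
| 2 from SOVA, 4 from MI BS | 0.55 to 0.57 |
| 3 from MI BS only | 0.59 to 0.63 |

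In the SOVA-only settings the week 1 contrast alone falls to 0.33 to 0.38 (3 lost) and 0.20 to 0.29 (6 lost), although week 1 was fully observed. A likelihood-based analysis of all observed values stayed at 0.49 to 0.51 throughout.

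**With baseline included.** A smaller simulation (200 trials) used baseline, week 1 and month 4, an assumed effect of 0.6, and 12 to 13 of 70 lost because of a large week 1 change. The week 1 contrast was 0.507 complete-case, against 0.591 both in the full data and in a mixed model. With independent loss it was 0.602 complete-case, against 0.612 in the full data.

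**The case against.** The strongest reply is that the plan does not say what this point fears. Section 3.2.5c allows other methods, so a mixed model is already permitted. No text says that incomplete subjects are deleted. That week 1 and month 4 enter one model with baseline is an inference from 3.2.5c and 3.2.9 read together; a separate baseline-to-week-1 comparison would keep every week 1 value. All of this stands, which is why the point is conditional. It does not remove the point: the ANOVA is the only specific method named, and an open alternative lets the choice be made after the data are seen.

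A reader might go further and infer that the plan deletes such subjects, that week 1 injury therefore disappears, and that the device contrast shrinks. The documents do not support this. Shrinkage needs loss linked to injury and either concentrated in the worse arm or governed by one rule that removes more subjects from that arm. Equal losses of the worst subjects in each arm left the contrast at about 0.50, and losses weighted to MI BS enlarged it. The case of 6 SOVA losses puts all of the plan's expected loss in one arm, after week 1 and for one reason, so it is an extreme. Early soreness would also not vanish from the trial: section 3.2.8 asks separately whether the device hurts or pinches, and 3.2.9 schedules user satisfaction at week 1. Section 3.2.5 lists tissue health as an aspect of fabrication, not as the trial's harm outcome.

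Finally, the mixed model's good showing is partly built in, because loss was generated from observed week 1 values, the condition under which likelihood methods are unbiased. Loss driven by unobserved month 4 values was not tested.

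**Conclusion.** The concern holds in conditional form. If the named ANOVA is run across all visits on complete cases, observed week 1 values are lost and the device contrast can be biased either way. Against an assumed true 0.50 SD, the contrast is 12% to 18% too small when the worst 6 of 70 leave under one rule (0.44/0.50 and 0.41/0.50). It is 18% to 48% too small when 3 to 6 leave SOVA only, and 10% to 26% too large when losses fall more on MI BS. It is unbiased when loss is random or balanced. The MI BS settings stop at 3 lost from that arm alone, so the upper range is not the mirror image of the lower.

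These sizes rest on assumed effects, correlation and dropout patterns. The documents give no dropout by arm, no reasons and no tissue-health rates, so they show what is possible, not what to expect. The 58 in the final analysis would fit a completers-only set but does not prove one.

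**What to change.** In section 3.2.5c, replace the method sentence with a likelihood-based mixed model for repeated measures. It should use all observed post-delivery visits of all randomised subjects, with the baseline tissue-health value as a covariate (the section calls for comparison with baseline), terms for device, visit and device by visit, an unstructured covariance and small-sample degrees of freedom. Use the generalised version if the index is binary or ordinal. Report the device difference with a confidence interval at week 1 and at month 4, and report dropout by arm and reason.

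The cost is a few lines of analysis text, a dropout table and no extra tissue-health measurements; reasons for leaving need to be recorded. The small downside is that the model assumes missingness depends only on observed values. The plan should state this; it is a weaker assumption than the complete-case ANOVA needs. The model cannot recover post-delivery information for subjects who leave before week 1.
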